8.3 MRI Sequences

Cerebral metabolic rate of oxygen (CMRO₂) MRI: To quantify absolute CMRO₂, both TRUST MRI for quantification of venous oxygenation (Yv) and phase contrast (PC) MRI for quantification of total flows are needed. The imaging details were described in our previous paper²². The total scan time for CMRO₂ MRI is approximately 4 minutes.

Resting-state functional MRI (RS-fMRI): The sequence parameters for the RS-fMRI scans follow the ADNI protocol. We will use a 2D EPI sequence with SENSE partial-parallel imaging acceleration to obtain 3.3×3.3 mm (64 by 64 voxels) in plane resolution in forty-eight 3.3 mm transverse slices. An ascending slice order with TR/TE = 3000/30 ms, flip angle of 75°, and SENSE acceleration factor of 2 will be used. SPIR will be used for fat suppression. We will record 140 time points, for a scan time of 7 min.

Regional brain perfusion -Pseudo-Continuous Arterial Spin Labeling (pCASL): Increased neural activity is known to increase local cerebral blood flow through neurovascular coupling, which can also be monitored with Arterial Spin Labeling (ASL)¹⁴⁷ technique before and after tDCS. The CBF measured with pCASL in the current study will be used as an exploratory marker of regional integrity of neurovascular coupling (i.e., CBF and Δ CBF in the PFC substrate) and its association with clinical and neuropsychological outcomes.

MRI session includes 2 conditions: tDCS off (immediately before and after tDCS) and active tDCS (in red frame) (refer to Figure 3). The RS-fMRI is performed before the active tDCS (with device turned off) to assess the network connectivity changes without any current influence. The pCASL is performed before and after the active tDCS (with device turned off) to assess the integrity of the brain regional perfusion. CMRO₂ scans include PC MRI for CBF and TRUST MRI for Yv estimation; both sequences are not sensitive to the current-induced field inhomogeneity.

8.4 Laboratory Procedures/Evaluations

N/A

CONFIDENTIAL

This material is the property of the NYU Langone. Do not disclose or use except as authorized in writing by the study sponsor
Observational Study Template Version: 8 February 2019

9 Safety and Adverse Events

9.1 Definitions

Unanticipated Problems Involving Risk to Subjects or Others

Any incident, experience, or outcome that meets all of the following criteria:

- Unexpected in nature, severity, or frequency (i.e. not described in study-related documents such as the IRB-approved protocol or consent form, the investigators brochure, etc)
- Related or possibly related to participation in the research (i.e., possibly related means there is a reasonable possibility that the incident experience, or outcome may have been caused by the procedures involved in the research)
- Suggests that the research places subjects or others at greater risk of harm (including physical, psychological, economic, or social harm).

Adverse Event

An **adverse event** (AE) is any symptom, sign, illness or experience that develops or worsens in severity during the course of the study. Intercurrent illnesses or injuries should be regarded as adverse events.

Abnormal results of diagnostic procedures are considered to be adverse events if the abnormality:

- results in study withdrawal
- is associated with a serious adverse event
- is associated with clinical signs or symptoms
- leads to additional treatment or to further diagnostic tests
- is considered by the investigator to be of clinical significance

Serious Adverse Event

Adverse events are classified as serious or non-serious. A **serious adverse event** is any AE that is:

- fatal
- life-threatening
- requires or prolongs hospital stay
- results in persistent or significant disability or incapacity
- a congenital anomaly or birth defect
- an important medical event

Important medical events are those that may not be immediately life threatening, but are clearly of major clinical significance. They may jeopardize the subject, and may require intervention to prevent one of the other serious outcomes noted above. For example, drug overdose or abuse, a seizure that did not result in in-patient hospitalization, or intensive treatment of bronchospasm in an emergency department would typically be considered serious.

All adverse events that do not meet any of the criteria for serious should be regarded as **non-serious adverse events**.

Preexisting Condition

A preexisting condition is one that is present at the start of the study. A preexisting condition should be recorded as an adverse event if the frequency, intensity, or the character of the condition worsens during the study period.

General Physical Examination Findings

At screening, any clinically significant abnormality should be recorded as a preexisting condition. At the end of the study, any new clinically significant findings/abnormalities that meet the definition of an adverse event must also be recorded and documented as an adverse event.

Post-study Adverse Event

CONFIDENTIAL

This material is the property of the NYU Langone. Do not disclose or use except as authorized in writing by the study sponsor
Observational Study Template Version: 8 February 2019

All unresolved adverse events should be followed by the investigator until the events are resolved, the subject is lost to follow-up, or the adverse event is otherwise explained. At the last scheduled visit, the investigator should instruct each subject to report any subsequent event(s) that the subject, or the subject's personal physician, believes might reasonably be related to participation in this study. The investigator should notify the study sponsor of any death or adverse event occurring at any time after a subject has discontinued or terminated study participation that may reasonably be related to this study. The sponsor should also be notified if the investigator should become aware of the development of cancer or of a congenital anomaly in a subsequently conceived offspring of a subject that has participated in this study.

9.2 Recording of Adverse Events

At each contact with the subject, the investigator must seek information on adverse events by specific questioning and, as appropriate, by examination. Information on all adverse events should be recorded immediately in the source document, and also in the appropriate adverse event module of the case report form (CRF). All clearly related signs, symptoms, and abnormal diagnostic procedures results should be recorded in the source document, though should be grouped under one diagnosis.

All adverse events occurring during the study period must be recorded. The clinical course of each event should be followed until resolution, stabilization, or until it has been determined that the study treatment or participation is not the cause. Serious adverse events that are still ongoing at the end of the study period must be followed up to determine the final outcome. Any serious adverse event that occurs after the study period and is considered to be possibly related to study participation should be recorded and reported immediately.

9.3 Reporting of Serious Adverse Events and Unanticipated Problems

For Narrative Reports of Safety Events

If the report is supplied as a narrative, the minimum necessary information to be provided at the time of the initial report includes:

- Study identifier
- Study Center
- Subject number
- A description of the event
- Date of onset
- Current status
- Whether study treatment was discontinued
- The reason why the event is classified as serious
- Investigator assessment of the association between the event and study treatment

9.3.1 Investigator reporting: notifying the IRB

Federal regulations require timely reporting by investigators to their local IRB of unanticipated problems posing risks to subjects or others. The following describes the NYULMC IRB reporting requirements, though Investigators at participating sites are responsible for meeting the specific requirements of their IRB of record.

Report Promptly, but no later than 5 working days:

Researchers are required to submit reports of the following problems promptly but no later than 5 working days from the time the investigator becomes aware of the event:

- ***Unanticipated problems including adverse events that are unexpected and related***
 - *Unexpected: An event is “unexpected” when its specificity and severity are not accurately reflected in the protocol-related documents, such as the IRB-approved research protocol, any applicable investigator brochure, and the current IRB-approved informed consent document and other relevant sources of information, such as product labeling and package inserts.*
 - *Related to the research procedures: An event is related to the research procedures if in the opinion of the principal investigator or sponsor, the event was more likely than not to be caused by the research procedures.*
 - *Harmful: either caused harm to subjects or others, or placed them at increased risk*

CONFIDENTIAL

This material is the property of the NYU Langone. Do not disclose or use except as authorized in writing by the study sponsor
Observational Study Template Version: 8 February 2019

Other Reportable events:

The following events also require prompt reporting to the IRB, though **no later than 5 working days**:

- **Complaint of a research subject** when the complaint indicates unexpected risks or the complaint cannot be resolved by the research team.
- **Protocol deviations or violations** (includes intentional and accidental/unintentional deviations from the IRB approved protocol) for any of the following situations:
 - *one or more participants were placed at increased risk of harm*
 - *the event has the potential to occur again*
 - *the deviation was necessary to protect a subject from immediate harm*
- **Breach of confidentiality**
- **Incarceration of a participant** when the research was not previously approved under Subpart C and the investigator believes it is in the best interest of the subject to remain on the study.
- **New Information indicating a change to the risks or potential benefits** of the research, in terms of severity or frequency. (e.g., analysis indicates lower-than-expected response rate or a more severe or frequent side effect; Other research finds arm of study has no therapeutic value; FDA labeling change or withdrawal from market)

Reporting Process

The reportable events noted above will be reported to the IRB using a Reportable New Information submission and will include a description of the event with information regarding its fulfillment of the above criteria, follow-up/resolution, and need for revision to consent form and/or other study documentation. Copies of each report and documentation of IRB notification and receipt will be kept in the Clinical Investigator's study file.

9.4 Classification of an Adverse Event

9.4.1 Severity of Event

For AEs not included in the protocol defined grading system, the following guidelines will be used to describe severity.

- **Mild** – Events require minimal or no treatment and do not interfere with the participant's daily activities.
- **Moderate** – Events result in a low level of inconvenience or concern with the therapeutic measures. Moderate events may cause some interference with functioning.
- **Severe** – Events interrupt a participant's usual daily activity and may require systemic drug therapy or other treatment. Severe events are usually potentially life-threatening or incapacitating.

9.4.2 Relationship to Study Intervention

The study PI, in conjunction with CO-I and clinicians, will determine the relationship of any adverse events or unanticipated problems to study procedures and equipment.

9.4.3 Expectedness

The study PI will be responsible for determining whether an AE is expected or unexpected. An AE will be considered unexpected if the nature, severity, or frequency of the event is not consistent with the risk information previously described for the study intervention.

9.5 Time Period and Frequency for Event Assessment and Follow-Up

The occurrence of an AE or SAE may come to the attention of study personnel during study visits and interviews of a study participant presenting for medical care, or upon review by a study monitor. All AEs including local and systemic reactions not meeting the criteria for SAEs will be captured on the appropriate

CONFIDENTIAL

This material is the property of the NYU Langone. Do not disclose or use except as authorized in writing by the study sponsor
Observational Study Template Version: 8 February 2019

RF. Information to be collected includes event description, time of onset, clinician's assessment of severity, relationship to study intervention (assessed only by those with the training and authority to make a diagnosis), and time of resolution/stabilization of the event. All AEs occurring while on study must be documented appropriately regardless of relationship. All AEs will be followed to adequate resolution.

Any medical condition that is present at the time that the participant is screened will be considered as baseline and not reported as an AE. However, if the study participant's condition deteriorates at any time during the study, it will be recorded as an AE. UPs will be recorded in the data collection system throughout the study.

Changes in the severity of an AE will be documented to allow an assessment of the duration of the event at each level of severity to be performed. AEs characterized as intermittent require documentation of onset and duration of each episode.

The PI will record all reportable events with start dates occurring any time after informed consent is obtained until participant completes study. [name] will be informed of the occurrence of SAEs, review the SAE with the PI and study team, and assess the event based on institutional guidelines regarding relatedness to the study, harm to the patient, or if it is expected. Events will be followed for outcome information until resolution or stabilization.

All unresolved adverse events should be followed by the PI as well as MD-Co Investigator until the events are resolved, the subject is lost to follow-up, or the adverse event is otherwise explained. The investigator should notify the study sponsor of any death or adverse event occurring at any time after a subject has discontinued or terminated study participation that may reasonably be related to this study.

9.6 Reporting Procedures – Notifying the IRB

9.6.1 Adverse Event Reporting

All adverse events will be reported to IRB per NYU policy.

9.6.2 Serious Adverse Event Reporting

All serious adverse events will be reported to IRB per NYU policy. Presence of an SAE will be included on data safety monitoring reports to the IRB and an immediate report (SAE that is related to study) will be submitted to the IRB within 48 hours of the event occurring. [name] will review all SAE reports prior to their submission and follow up with each patient.

9.6.3 Unanticipated Problem Reporting

Incidents or events that meet the OHRP criteria for UPs require the creation and completion of an UP report form. It is the site investigator's responsibility to report UPs to their IRB. The UP report will include the following information:

- Protocol identifying information: protocol title and number, PI's name, and the IRB project number;
- A detailed description of the event, incident, experience, or outcome;
- An explanation of the basis for determining that the event, incident, experience, or outcome represents an UP;
- A description of any changes to the protocol or other corrective actions that have been taken or are proposed in response to the UP.

To satisfy the requirement for prompt reporting, UPs will be reported using the following timeline:

- UPs that are SAEs will be reported to the IRB within 10 days of the investigator becoming aware of the event.

CONFIDENTIAL

This material is the property of the NYU Langone. Do not disclose or use except as authorized in writing by the study sponsor
Observational Study Template Version: 8 February 2019

- All UPs should be reported to appropriate institutional officials (as required by an institution's written reporting procedures), the supporting agency head (or designee), and OHRP within 10 days of the IR's receipt of the report of the problem from the investigator.

9.6.4 Reporting of Pregnancy

In the case of a positive pregnancy test, the participant will be informed of the test results and excluded from participating in the study.

10 Study Oversight

10.1 Safety Oversight

It is the responsibility of the Principal Investigator and [name] to oversee the safety of the study. This safety monitoring will include careful assessment and appropriate reporting of adverse events as noted above, as well as the construction and implementation of a site data and safety-monitoring plan.

Data safety monitoring will occur at least on a tri-annual (3 times a year) basis and will include PI and [name] review of safety and efficacy data including reports of tDCS side effects including skin irritation, itching, warming, and discomfort, potential distress from completing cognitive assessments and questionnaires, protocol adherence, regulatory documentation, enrollment (e.g. rate of enrollment, screen fails, withdrawals, etc.), unanticipated problems, and any issues that may arise during the course of research. Data safety monitoring reports will be submitted to the IRB on an annual basis at the time of continuing review. There are no predefined stopping rules.

10.2 Medical monitoring

[name], MD, Director of the NYU MSCCC, will serve as medical monitor for this study. [name] will be responsible for assessing the severity and relatedness of SAEs. In addition, [name] will be responsible for communicating incidental findings that have clinical significance found on the MRI scans to the patient.

10.3 Study Halting Rules

There are no predefined study halting rules.

10.4 Clinical Monitoring

Not Applicable

11 Statistical Considerations

11.1 Study Hypotheses

For the first aim with a cross-sectional representative cohort data, we hypothesized that higher IIV predicts a clinical classification of early cognitive impairment. For the second aim with longitudinal observational early MS cohort, we predict that higher IIV at baseline will predict greater decline. For the last aim with prospective recruitment of a prodromal cohort, we predict that that CMRO₂ response to tDCS to DLPFC will differentiate at-risk patients with high vs. low IIV.

11.2 Sample Size Determination

We aim to enroll 60 participants with prodromal MS to have n=50 evaluable participants (30 evaluable for the tDCS-MRI group and 20 evaluable for cognitive assessment group). As this is an exploratory protocol that is collecting data for future power analyses, the designation of recruiting 60 human subjects is arbitrary. Showing the feasibility of using Cogstate by this initial sample of participants, future studies can be conducted with properly powered samples to build a larger database. Recruitment of 60 participants would allow for enough data for assessing feasibility.

CONFIDENTIAL

This material is the property of the NYU Langone. Do not disclose or use except as authorized in writing by the study sponsor
Observational Study Template Version: 8 February 2019

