Participant Duration	Participation will include one visit that will last approximately 1.5-3.5 hours and will include a cognitive assessment, optional gait assessment. 35 participants will have a 60-minute MRI combined with simultaneous tDCS after the cognitive assessment. Participants may complete the MRI during a second visit.
Population	We will recruit 50 adults with early (prodromal) MS (e.g., clinically isolated syndrome (CIS), radiologically isolated syndrome (RIS), or subjects with a MS diagnosis of less than 5 years).
Study Sites	
• [name] – NYU Dept. of Neurology• [name] – NYU Multiple Sclerosis Comprehensive Care Center• NYU Langone Bernard and Irene Schwartz Center for Biomedical Imaging (CBI): [name]
Number of participants	N= 60
Statistical Analysis	Descriptive statistics, repeated measures ANOVA, simple correlations, and regression

CONFIDENTIAL

This material is the property of the NYU School of Medicine and Langone Medical Center. Do not disclose or use except as authorized in writing by the study sponsor

Drug/Device Template Version: 8 February 2019

Schematic of Study Design

CONFIDENTIAL

This material is the property of the NYU Langone. Do not disclose or use except as authorized in writing by the study sponsor
Observational Study Template Version: 8 February 2019

1 Key Roles

[name], PhD
Department of Neurology, NYU Langone Health
[name]
[name]
[contact]

[name], M.D.
Department of Neurology, NYU Langone Health
[name]
[name]
[contact]

[name].
NYU Langone Health —Radiology
[name]
[name]
[contact]

[name]
Department of Neurology, NYU Langone Health
[name]
[contact]
[contact]

[name]
Department of Neurology, NYU Langone Health
[name]
[contact]
[contact]

2 Introduction, Background Information and Scientific Rationale

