6.1 Inclusion Criteria for All Participants

In order to be eligible to participate in this study, an individual must meet all of the following criteria:

1. Ages 21-59 years old (inclusive)
2. Prodromal MS (defined by radiologically isolated syndrome \leq 6 months from first MRI or clinically isolated syndrome \leq 3 months from first clinical event)
3. MS diagnosis of \leq than 5 years

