11.3 Statistical Methods

For the cognitive measures, the scores will be transformed to z scores to adjust for age: Each individual IIV value will be transformed into an age-normative z score using the Cogstate normative database (n=95,162). This will result in an age-adjusted IIV z score for use in all analyses described below.

BICAMS tests of SDMT, RAVLT and BVMT-R will be similarly converted to age-normative z scores using the most recently available databases¹³³⁻¹³⁶. A single BICAMS score will be computed as the average of z scores across the three measures⁴⁹.

Baseline patient and disease characteristics will be summarized for the 60 participants enrolled into this cohort. The primary focus in this cohort is to evaluate IIV along with changes in CMRO₂ during stimulation as described above as predictors of disease status. Distributions of IIV values and CMRO₂ at baseline and during stimulation, along with changes in CMRO₂ will be summarized descriptively and graphically with BICAMS classes. Bivariate scatterplots will display the baseline, during, and changes with IIV levels. Pairwise correlations will be estimated as measures of association between these variables (with transformations of values if required). Based on prior data, the mean change from baseline in CRMO₂ in 31 patients =7.91, sd=10.17 (mean % change =5.61%, sd=6.72). Here, we will predict IIV based on the CMRO₂ measurements at baseline and in response to tDCS. Other covariates will be incorporated into these exploratory models. For the binary BICAMS classes, again AUCs for the ROC curves from logistic models will be used to evaluate the roles of CRMO₂ changes and IIV. Sample size. With 50 evaluable participants, we can detect an R² \geq 0.141 from a univariable regression model and of 0.225 with 5 independent variables. The collected data for this prodromal cohort will serve as the basis for future longitudinal follow-up of this cohort.

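### Section 11 calls the whole pooled cohort prodromal, but section 6.1 reserves that term for recent RIS or CIS, and no analysis by diagnostic group is named, so a pooled result cannot be attributed to prodromal MS

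*Combined protocol and SAP*

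**What the plan says.** **Definition.** Section 6.1, criterion 2, opens "Prodromal MS (defined by radiologically isolated syndrome" and sets the limits at 6 months from first MRI for RIS and 3 months from first clinical event for CIS. Criterion 3 is a separate line for MS diagnosed up to 5 years ago. The lead-in to the list says that "an individual must meet all of the following criteria".

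**Summary.** The Population row of the Protocol Summary uses one label for early and prodromal MS and gives as examples "clinically isolated syndrome (CIS), radiologically isolated syndrome (RIS), or subjects with a MS diagnosis of less than 5 years". Section 8.1.1 also treats the MS route and the prodromal route as alternatives, and explains how people diagnosed under five years ago can document eligibility.

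**Section 11.** The third aim in 11.1 refers to a prodromal cohort. Section 11.2 says "We aim to enroll 60 participants with prodromal MS to have n=50 evaluable participants", split as "30 evaluable for the tDCS-MRI group and 20 evaluable for cognitive assessment group". Section 11.3 ends: "The collected data for this prodromal cohort will serve as the basis for future longitudinal follow-up of this cohort".

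**Analysis.** Section 11.3 names age-normed z scores, a summary of disease characteristics, pairwise correlations, regressions of IIV on CMRO2, and ROC curves for BICAMS classes. It allows further covariates without naming them. Section 11.3.1 adds a socioeconomic indicator. Diagnostic group is named in none of these. No section sets a quota or minimum for RIS/CIS.

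**The concern.** The summary objective is IIV as a marker of prodromal MS, and section 2.2 puts the interest in risk before disability appears. By the definition in section 6.1, the label used in section 11 is wrong for everyone who enters with diagnosed MS. A sample with few or no RIS/CIS participants would comply with the plan, and its pooled result would still be reported as a finding in a prodromal cohort. Section 11.3 makes this cohort the base for later follow-up, so the label would carry forward.

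A second, smaller issue is confounding. If IIV and CMRO2 response (or BICAMS) both shift between RIS/CIS and diagnosed MS, pooling creates some association between them even when there is none within either group.

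**Working it through.** **1. The labels side by side**

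| Place | How the population is described |
|---|---|
| Summary, Population | early and prodromal treated as one; CIS, RIS *or* MS under 5 years |
| 4.1 | prodromal/early MS |
| 6.1 | prodromal = RIS ≤6 months or CIS ≤3 months; MS ≤5 years listed separately; *all* criteria required |
| 8.1.1 | MS route or prodromal route |
| 11.1, 11.2, 11.3 | prodromal, for the whole cohort |

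Section 11.1 also calls its second-aim cohort early MS and its third-aim cohort prodromal, so section 11 itself uses the two terms for different cohorts. Read literally, 6.1 asks for criteria 2 and 3 together, which conflicts with the summary and with 8.1.1.

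**2. The plan's detectable R²**

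The plan states 0.141 (one predictor) and 0.225 (five predictors) with 50 evaluable. Alpha and power are not stated; I assume 0.05 and 80%. For the overall F test, the noncentrality is λ = nR²/(1−R²).

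- n = 50, one predictor: λ = 50 × 0.141/0.859 = 8.21, power 80.2%.
- n = 50, five predictors: λ = 50 × 0.225/0.775 = 14.52, power 80.0%.

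The figures reproduce, but for the pooled 50. CMRO2 is measured only in the tDCS-MRI group (30 evaluable). There the detectable R² is 0.219 and 0.349, and power at the stated values is 57% and 50%.

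**3. What RIS/CIS alone could show**

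The share is not given, so it is varied. The half-width of the 95% interval for mean IIV z is t(0.975, n−1)/√n, in within-group SD units. Detectable R² is for one predictor, under the assumptions of step 2.

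| RIS/CIS of 50 | Half-width | Detectable R² |
|---|---|---|
| 5 | 2.776/√5 = 1.24 | 0.78 |
| 10 | 2.262/√10 = 0.72 | 0.51 |
| 15 | 2.145/√15 = 0.55 | 0.38 |

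Within the 30 tDCS-MRI participants, detectable R² is 0.70 with 6 RIS/CIS (20%) and 0.38 with 15 (50%).

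**4. Association produced by pooling**

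Let p be the RIS/CIS share and d the group difference in within-group SDs, equal on both measures, with no association within group. The pooled correlation is r = p(1−p)d²/[1 + p(1−p)d²]. The values of d are assumptions.

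| p | d | r | r² |
|---|---|---|---|
| 0.2 | 0.8 | 0.1024/1.1024 = 0.09 | 0.009 |
| 0.5 | 0.8 | 0.16/1.16 = 0.14 | 0.019 |
| 0.2 | 1.0 | 0.16/1.16 = 0.14 | 0.019 |
| 0.5 | 1.0 | 0.25/1.25 = 0.20 | 0.040 |

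By Fisher's z, the chance of p < 0.05 from this artefact follows from a normal deviate with mean atanh(r)√(n−3).

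- n = 30 (IIV–CMRO2): mean 0.48 to 1.05, chance 8% to 18%.
- n = 50 (IIV–BICAMS): mean 0.64 to 1.39, chance 10% to 28%.

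**5. Price of adding diagnostic group**

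For one tested predictor, detectable partial R² moves from 0.1405 to 0.1406 at n = 50 and from 0.2192 to 0.2197 at n = 30. This counts the lost degree of freedom only. If group and CMRO2 response are correlated, the adjusted estimate is also less precise.

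**The case against.** **The documents also use the term more loosely.** The title speaks of prodromal disability in MS, the Population row openly includes MS under 5 years, and section 4.1 says prodromal/early MS. On that reading a recently diagnosed person without disability belongs to the target population. This stands. A reader might infer that the objective cannot be answered at all; the documents do not support that, because an early-MS question remains answerable.

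**Adjustment is not ruled out.** Section 11.3 provides for unnamed covariates and sizes a five-variable model, so it would be wrong to say that no analysis will adjust for stage. What holds is that stage is not named. The pairwise correlations are not described as adjusted for anything beyond age norming.

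**The mix is unknown.** A reader might infer from windows of 3 to 6 months against 5 years, and from recruitment at an MS centre, that most participants will have diagnosed MS. That is possible, but no expected mix or referral figure is given, so it cannot be shown.

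**The confounding is modest and its inputs are assumed.** An induced r² of 0.04 or less is well below the plan's 0.141.

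**Adjustment may remove signal.** Section 4.1 is about mechanism. If IIV and CMRO2 change together as disease advances, that may be what is sought. This argues against making the adjusted model the only one. Time since first event or diagnosis is a poor required covariate: its origin differs by group, and it is nearly collinear with group because RIS and CIS are capped at 6 and 3 months.

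**The study is exploratory, with a sample size that it calls arbitrary.** That lowers the stakes but does not excuse a population label that contradicts the eligibility section.

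**Conclusion.** The point holds as one of labelling and pre-specification. Section 11 gives the whole pooled sample a name that section 6.1 confines to recent RIS or CIS, nothing secures a minimum number of such participants, and no analysis by diagnostic group is named. Pooled results can speak to early MS; they cannot be attributed to prodromal MS as section 6.1 defines it.

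The main harm is a misattributed conclusion. With 5 to 15 RIS/CIS participants of 50, their mean IIV z would be known only to within 1.24 to 0.55 SD, and only R² of 0.78 to 0.38 would be detectable in them. Those shares are assumptions. Spurious association from mixing stages is secondary: r of about 0.09 to 0.20, resting on assumed differences of 0.8 to 1.0 SD on both measures. The change should be made, since it alters what the study may conclude at almost no cost.

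**What to change.** 1. In 11.1 to 11.3, describe the prospective cohort as early MS (RIS, CIS or MS up to 5 years).
2. Reconcile the requirement in 6.1 that all criteria be met with the *or* in the summary Population row.
3. In 11.3, report IIV, CMRO2 and BICAMS by diagnostic group (RIS/CIS versus MS) with confidence intervals.
4. Beside each unadjusted IIV–CMRO2 and IIV–BICAMS model, add a sensitivity version with diagnostic group as a covariate, and state that the CMRO2 models rest on about 30 evaluable participants. Do not require time since first event or diagnosis.
5. Allow prodromal-specific conclusions only from the RIS/CIS estimates.

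Diagnosis is already confirmed at eligibility, so no new visit or test is needed. The cost is about one degree of freedom in the sensitivity model, some precision if group is related to the predictors, and a more modest prodromal claim.
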